There is a difference between ultrasound guided Pericapsular Nerve Group Block and ultrasound guided Fascia Iliaca Block as a regional analgesic techniques for pre- and post-operative analgesia in elderly patients with hip fracture.

Aim of the work

The aim of the present study is to improve quality of pain control in the pre- and post-operative periods in elderly patients with hip fracture.

Objectives

1. To compare the time of performance and the analgesic effect in the pre- and post-operative periods between ultrasound guided Pericapsular Nerve Group (PENG) block, fascia iliaca block and intravenous fentanyl (control group).
2. To assess the quality of patient's positioning during performance of spinal anesthesia by operator satisfaction score.
3. To assess time of onset of postoperative ambulation.

Patients and Methods

I. Technical design:

● **Site of the study:**

This study will take place at Zagazig University Hospitals after approval of Institutional Review Board (IRB).

● **Duration of the study:**

Two years.

● **Sample size:**

Assuming that mean \pm SD for VAS scores at positioning for spinal anesthesia in intravenous fentanyl versus fascia iliaca block were 3.5 ± 2.5 versus 2.1 ± 0.9 [4] with confidence level 95% and power of test 80%.

The total sample size is 51 (17 in each group) calculated by OpenEpi[®].

● **Inclusion criteria:**

1. Patient acceptance.
2. Accepted mental state of the patient.
3. Gender: both sexes.
4. Age above 65 years old.
5. Body mass index 18.5-35 kg/m².
6. ASA physical status II and III.
7. Unilateral hip fracture assigned for surgical fixation.
8. Expected duration of surgery \leq 3 hours.

● **Exclusion criteria:**

1. Associated trauma or multiple fractures.
2. Peripheral neuropathy.
3. Coagulopathy.
4. Infection at site of injection.
5. Allergy to the drugs used in the study.
6. Advanced kidney, liver or heart disease.

- **Withdrawal criteria:**

The patient has the right to withdraw from the study at any time without any negative consequences on their medical or surgical treatment plan.

II. Operational design:

- **Type of the study:**

This study is a randomized double-blind controlled clinical trial.

- **Parameters of the study:**

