All patients will be visited on the day before surgery at the ward, for all patients a full history (personal, medical and family) will be taken, physical examination will be done. We will order a full laboratory work up: complete blood picture (CBC), kidney function tests (KFTs), liver function tests (LFTs), random blood sugar (RBS), prothrombin time (PT), partial thromboplastin time (PTT), international normalized ratio (INR), serum electrolytes and 12-lead ECG and the results will be revised. We will order any consultation required to prepare the patient (cardiology consultation will be done routinely).

Explanation of the whole procedure to the patient and a written informed consent will be obtained. Instructions will be given for preoperative fasting (6 hrs for light meals and 2 hrs for clear fluids). Visual analogue score for pain will be explained to all patients.

An intravenous cannula will be inserted for preoperative medications and blood sample will be sent for blood group matching to insure availability of blood of the same group before the operation.

On the day of surgery one hour before the operation, all patients will receive intravenous pantoprazole 40 mg and cefotaxime 1 gm.

On arrival to the operating room:

1. Monitoring: Standard operative monitoring will be applied to all patients including electrocardiogram (ECG), peripheral pulse oximeter and non-invasive blood pressure (NIBP). Basal readings of heart rate (HR), mean arterial pressure (MAP), oxygen saturation (SpO₂) and body temperature will be recorded.
2. Fluid preloading: Lactated ringer in a dose of 6 ml/kg over 30 minutes.
3. Revision on the resuscitation equipment including anesthetic machine, ventilator, face mask, oral airway, laryngeal mask, laryngoscope, endotracheal tubes, DC shock and drugs as atropine, ephedrine, hydrocortisone, antihistaminic, epinephrine and general anesthesia induction drugs.
4. Each patient will be asked for (his/her) pain by visual analogue pain score during rest and we will do the 15 degrees leg raising test and record VAS, heart rate and mean blood pressure both during rest and 15 degrees leg raising test. The records will be done by the anesthesiologist responsible for administration of spinal anesthesia and blinded to the groups' assignment.

● **Equipment:**

○ **Ultrasound:**

Mindray diagnostic ultrasound system, model: M5, SN: MR-55006765. Made in China.

○ **Transducers:**

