- Mindray high frequency transducer, model: 10L4s, SN:MLW3C101256. Made in China.
- Mindray low frequency transducer, model: C5-2s, SN: NDX54023456. Made in China.

○ **Needle for performing the block:**

22-gauge, 80-mm Quincke spinal needle.

- **Needle for spinal anesthesia:**

25-gauge, Quincke spinal needle.

- **Local anesthetics:**

Bupivacain 0.5% diluted to 0.25% solution and magnesium sulphate as an additive for regional blocks and heavy bupivacaine 0.5% for spinal anesthesia.

- **Randomization:**

Patients will be randomly allocated by computer generated randomization table into three equal groups (17 patients each):

Group C (Control group):

Control group (n=17): Patients will be assigned to receive opioids analgesia before spinal anesthesia in the form of intravenous fentanyl in a dose of 1mic/kg divided into two boluses with 5 minutes interval in between before positioning the patient for spinal anesthesia.

Group P:

PENG block group (n=17): Patients will be assigned to receive Pericapsular Nerve Group Block (PENG Block) before positioning the patient for spinal anesthesia.

After disinfection of the skin from the anterior superior iliac spine (ASIS) to the inguinal ligament with alcohol on the affected side, sterile drapes will be used to surround the area of the block. While the patient in the supine position, a curvilinear low-frequency ultrasound probe (2–5MHz) will be first placed in a transverse plane over the anterior inferior iliac spine (AIIS), then rotated caudally about 45 degrees to be aligned with the pubic ramus. At this point the view on the screen will be viewing from medial to lateral; the pectineus muscle, the femoral artery, the iliopectineal eminence (IPE), the iliopsoas muscle and tendon and the AIIS. A 22-gauge, 80-mm spinal needle will be inserted from lateral to medial in an in-plane approach to place the tip in the musculofascial plane between the psoas tendon anteriorly and the pubic ramus posteriorly. After negative aspiration, the local anesthetic solution will be injected in 5-

mL increments while observing for adequate fluid spread in this plane for a total volume of 20 mL of 0.25% bupivacaine + 250 mg magnesium sulphate. A hypoechoic expanding shadow should be visualized between the psoas tendon and the pubic ramus indicating proper site of injection [16].

Group F:

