Fascia Iliaca block group (n=17): Patients will be assigned to receive Fascia Iliaca Block (F.I Block) before positioning for spinal anesthesia.

After disinfection of the skin over the upper thigh with alcohol on the affected side, sterile drapes will be used to surround the area of the block. While the patient in the supine position, a linear high-frequency ultrasound probe (10–15MHz) will be placed in the inguinal crease to identify the femoral artery and vein in the short axis. Then the ultrasound probe will be slid laterally while identifying the psoas muscle until the most anterior position of the curve of the psoas muscle is identified. A 22-gauge, 80-mm needle is inserted and advanced using an in-plane technique until the tip of the needle is positioned at that point, noting the ‘pop’ through the fascia lata and fascia iliaca. A small test injection is made to ensure that the fluid is seen to lift the fascia iliaca and flow between the fascia and the psoas muscle. After negative aspiration, 30 mL of 0.25% bupivacaine + 250 mg magnesium sulphate is injected in 5 mL increments under ultrasound visualization, with repeating test aspiration after every 5 mL. An expanding anechoic collection just below the fascia iliaca separating it from the psoas muscle should be certainly visualized indicating correct placement of anesthetic solution [17].

In the three groups, the onset of analgesia will be detected by 15 degrees leg raising test and will be recorded. The 15 degrees leg raising test will be used after 10 minutes from injection of local anesthetic in the groups received regional analgesia and after 2 minutes from intravenous injection in the fentanyl group. While the patient is supine, we will try to passively elevate the patient’s leg on the affected side for 15 degrees. If the patient complains of intolerable pain on moving his leg, the test will be aborted and we will wait for a minute before repeating the test. The test will be repeated every minute until we detect the onset of the analgesia that will be represented by dynamic VAS ≤ 4 . For all patients visual analogue pain

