score (VAS) is used to evaluate pain. VAS is done by drawing a 10cm vertical line on a piece of paper with its limits “no pain” (0) on one side and “extreme pain” (10) on the other side. The patient will be asked to point where the pain (he/she) experiences lies on the line and the score is recorded ^[18]. Patient will be asked to evaluate his pain on VAS scale before and after the analgesic technique (starting 10 minutes after regional blocks and repeated every minute and 2 minutes after fentanyl injection). Once $VAS \leq 4$, patient will be positioned to receive spinal anesthesia. Vital signs will be recorded with each VAS reading.

Administration of spinal anesthesia:

After analgesia is established and fluid preload is given, patient’s position will be changed to sitting position to receive spinal anesthesia. Spinal anesthesia will be administered by an anesthesiologist who is blinded to groups’ assignment.

Anesthesiologist’s satisfaction with patient’s positioning will be evaluated by operator satisfaction score ; 0=unsatisfactory, 1=satisfactory, 2=good or 3=optimal ^[4]. This scoring will be done by the anesthesiologist responsible for spinal anesthesia administration.

During patient positioning for spinal anesthesia, VAS and vital signs (HR, MAP, SpO₂ and body temperature) will be recorded. If a patient reports $VAS \geq 4$ during positioning, the procedure will be stopped, the patient will be recorded as a failure rate and 1 mic/kg of i.v. fentanyl will be administered in any group. Positioning will be reattempted after VAS is reduced to <4.

After patient is in the sitting position, sterilization of the skin of the back will be done by 10% betadine then sterile drapes are used to surround the area of injection. Then 2 cc of 2% lidocaine will be injected to anesthetize the skin and subcutaneous tissue by forming a skin wheel. Spinal anesthesia will be performed by paramedian approach in the intervertebral space (L3/L4) using a 25G Quincke spinal needle with the bevel directed laterally. After correct needle placement in the subarachnoid space which is confirmed by free flow of cerebrospinal fluid (CSF), 2.5 cc of 0.5% hyperbaric bupivacaine (12.5 mg) + 25 mic fentanyl will be

injected in the subarachnoid space and the needle will be extracted. The skin will be dressed and the patient will be placed in the supine position and oxygen will be supplied by a facemask.

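### The double-blind label does not fit either fentanyl-versus-block comparison: patients cannot be blinded there, and the only role named as blinded is the anesthesiologist giving the spinal

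*Protocol*

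**What the plan says.** Under Operational design, Type of the study, the protocol says: "This study is a randomized double-blind controlled clinical trial". That sentence names no roles. Two other places name one. In item 4 of the steps on arrival to the operating room, for the baseline pain readings, "The records will be done by the anesthesiologist responsible for administration of spinal anesthesia and blinded to the" groups' assignment. Administration of spinal anesthesia repeats that this anesthesiologist is blinded, and the same person scores operator satisfaction.

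The treatments are set out under Randomization. For Group C, "Patients will be assigned to receive opioids analgesia before spinal anesthesia in the form of intravenous fentanyl", in two boluses five minutes apart. The Group P text begins "After disinfection of the skin from the anterior superior iliac spine (ASIS) to the inguinal ligament with alcohol on the affected side" and goes on to drapes, an ultrasound probe and a needle. The Group F text begins "After disinfection of the skin over the upper thigh with alcohol on the affected side, sterile drapes will be used to surround the area" and follows the same pattern.

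Pain is self-reported: "The patient will be asked to point where the pain (he/she) experiences lies on the line and the score is recorded". The sample size paragraph assumes that "VAS scores at positioning for spinal anesthesia in intravenous fentanyl versus fascia iliaca block were" 3.5 (SD 2.5) and 2.1 (SD 0.9). At the visit the day before surgery, "Explanation of the whole procedure to the patient and a written informed consent will be obtained".

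**The concern.** A reader will normally take an unqualified double-blind label to cover the patient and at least one assessor, for every comparison in the trial. Objective 1 compares three arms, and the control arm differs from the other two in a way that a conscious patient cannot miss. Knowing whether a block was given can shift a self-marked pain score in either direction, and with it every event that the score triggers. If the label stands, the report could claim protection against this that the design does not give, including for the comparison on which the trial was sized.

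**Working it through.** No bias can be calculated from the document. The check is to compare what each party would know, contrast by contrast.

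**1. What the patient experiences**

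| | Group C | Group P | Group F |
|---|---|---|---|
| Intravenous fentanyl boluses before positioning | yes | not described | not described |
| Skin disinfection and drapes at the groin or thigh | not described | yes | yes |
| Ultrasound probe | not described | curvilinear | linear |
| 22-gauge, 80-mm needle | not described | yes | yes |
| Volume injected, in 5 mL steps | none | 20 mL | 30 mL |
| Sham, dummy injection, screen or sedation | none described | none described | none described |

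That patients are awake is an inference, but a safe one. They rate their own pain before and after the technique, report pain during the leg-raise test, and no sedative is listed.

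**2. The three contrasts**
- Fentanyl versus PENG: the patient knows whether a block was given. Not patient-blinded.
- Fentanyl versus fascia iliaca: the same. Not patient-blinded.
- PENG versus fascia iliaca: both arms have disinfection, drapes, probe and needle. Patient blinding is possible but not stated.

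So 2 of 3 contrasts are affected.

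**3. The sized contrast**

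The sample size rests on fentanyl versus fascia iliaca: 17 + 17 = 34 patients, with a planned difference of 3.5 − 2.1 = 1.4 on a 10 cm line that the patient marks. The stated inputs do not reproduce 17 per group. At two-sided 5% and 80% power, (2.5² + 0.9²) × (1.96 + 0.84)² / 1.4² ≈ 28.3, which rounds up to 29. That is a separate matter, and nothing here depends on it.

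**4. Outcomes exposed in the fentanyl contrasts**
- VAS at 7 or more times after treatment: after the technique (1, possibly repeated), at positioning (1), and at 2, 4, 6, 12 and 24 hours (5).
- Outcomes derived from or triggered by VAS: onset (VAS ≤ 4), positioning failure (VAS ≥ 4), and rescue, both time to first rescue and 24-hour consumption (VAS ≥ 4, a complaint of pain, or a patient request).
- Patient satisfaction, rated directly.

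These are largely one measurement seen several ways, not independent channels of bias.

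**5. What the assessor knows**

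The leg-raise test starts 2 minutes after fentanyl but 10 minutes after a block (end of the Group F text, repeated under Collecting data). Anyone present for the timed tests can tell fentanyl from block. No recorder is named for the post-technique, positioning or ward VAS; the protocol uses the passive voice or 'we'. The blinded anesthesiologist is tied by name only to the baseline readings, the spinal and the operator satisfaction score.

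**The case against.** Four objections deserve an answer.

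**The protocol does say who is blinded.** This stands. A reader of the quoted sentence alone might infer that nobody is identified, but two other places name the spinal anesthesiologist. The defect is that the label implies a second blinded party who is never identified.

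**The protocol never claims that patients are blinded.** This also stands: no sentence says so, and the document does not support the charge that it makes an explicit false claim about patients. But the label is unqualified, covers all three arms, and has no identified second party, so it remains unsupported for the fentanyl contrasts.

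**The hypotheses concern PENG versus fascia iliaca.** True, and that contrast lacks the block/no-block cue. It would be wrong to infer that the trial's stated hypothesis is undermined. The fentanyl contrasts still matter, because objective 1 includes the control arm and the sample size rests on one of them.

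**The counts show exposure, not harm.** Agreed. A reader might infer that the 1.4-point planned difference is partly expectation, or that the blocks will be favoured. The document gives no basis for a size or a direction.

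The preoperative explanation should not be over-read either. It covers the whole procedure the day before surgery, and nothing says that the allocated arm is disclosed.

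**Conclusion.** The label is unsupported for fentanyl versus PENG and for fentanyl versus fascia iliaca: 2 of 3 contrasts, including the sized one with its 34 patients and self-marked outcome. It is neither shown nor ruled out for PENG versus fascia iliaca. Blinding of assessors is documented for one role only, and the 2-versus-10-minute test schedule defeats it for onset readings in the fentanyl contrasts.

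This rests on two assumptions: patients are conscious during the technique, and no sham or screen is used beyond what is written. If either is wrong, the protocol should say so. The point should be corrected, because a stated design property is one that the described procedures cannot deliver. It is a matter of claim and interpretation; it does not show that any result would be biased.

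**What to change.** 1. Replace the double-blind label with a statement by contrast. Say that the two fentanyl contrasts are not patient-blinded. Say also that VAS, the outcomes derived from or triggered by it (onset, positioning failure, rescue) and patient satisfaction are interpreted there as open to expectation bias.
2. Claim patient blinding for PENG versus fascia iliaca only if a rule is added that staff do not tell patients which block they received.
3. Name the recorder of each outcome and state whether that person knows the allocation:
   - Keep the spinal anesthesiologist away from the analgesic technique and the timed onset tests, and have that person record VAS and operator satisfaction at positioning.
   - Report onset and post-technique VAS as not assessor-blinded for fentanyl versus block.
   - Have existing ward staff who are not told the allocation record the 2 to 24 hour VAS and rescue.

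The cost is wording, one communication rule and one workflow rule. No extra staff are needed, and the analysis, sample size and treatments are unchanged. The downsides should be stated openly: the blinding claim for the fentanyl contrasts becomes weaker, onset is read by someone who knows the allocation, and a patient may still disclose what was done. Patient expectation also remains. Removing it would need a sham, which is not asked for here.

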- In the elderly parenteral fentanyl may cause delirium or respiratory depression. Delirium can be assessed using the confusion assessment method (CAM). The CAM diagnostic algorithm is based on four cardinal features of delirium: 1) acute onset and fluctuating course, 2) inattention, 3) disorganized thinking, and 4) altered level of consciousness. A diagnosis of delirium according to the CAM requires the presence of features 1, 2, and either 3 or 4 [20].

At the end of the procedure patient will be asked to evaluate the analgesic technique used by patient's satisfaction score: Patient will be asked to rate his satisfaction with the technique of analgesia used by giving a score on a 1-3 scale (1 = unsatisfactory analgesia, 2 = satisfactory analgesia, 3 = excellent analgesia) [21].

In the recovery room: Patient will receive 1 gm paracetamol and 30 mg ketorolac by intravenous infusion as a part of standard multimodal analgesia.

In the ward: Postoperative standard analgesia will continue in the form of 1gm paracetamol/8hours and ketorolac 30 mg/12hours. Patient will be monitored for vital signs (HR, MAP, SpO₂ and body temperature), time of offset of spinal anesthesia (time from end of intrathecal injection of hyperbaric bupivacaine till recovery of the lower limbs motor power indicated by achieving grade 0 on modified bromage scale and fine touch sensation indicated by sensing pin brick) and postoperative pain by VAS score. Vital signs and VAS will be recorded at 2, 4, 6, 12 and 24 hours postoperative.

If patient gives VAS \geq 4 or complains of intolerable pain, a rescue analgesia will be given in the form of nalbuphine 0.1 mg/kg. We will record time of first rescue analgesia (the time between complete injection of the local anesthetic in the regional groups or fentanyl injection and the first analgesia requested by the patient), total postoperative rescue analgesic consumption in first 24 hours and time of onset of postoperative ambulation.

• **Collecting data:**

From each patient the following data will be collected:

- Patient characteristics (name, age, gender, body mass index (BMI), ASA grade).
- Fracture type.
- Type and duration of surgery (time from end of skin preparation till suturing the wound).

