- Physical examination (mental status, decubitus, chest, abdomen, neurological and examination of the site of injection), laboratory investigations (complete blood count, random blood sugar, international normalized ratio, prothrombin time, partial thromboplastin time, kidney functions tests, liver functions tests and serum electrolytes).
- Vital signs (heart rate, mean blood pressure, respiratory rate, temperature and SpO₂). Vital signs will be recorded before and after the analgesic technique, during positioning for spinal anesthesia and then every 10 minutes till the end of the surgery. Then we will record vital signs at 2, 4, 6, 12 and 24 hours postoperative.
- Intraoperative total fluids given, blood loss and urine output.
- Visual analogue pain score will be recorded before and after analgesic technique used (starting 10 minutes after regional blocks and repeated every minute and 2 minutes after fentanyl injection) and during positioning. VAS will be also recorded at 2, 4, 6, 12 and 24 hours postoperative.
- Time of block performance (time from the end of skin sterilization till end of injection of local anesthetic).
- Onset time of the analgesic technique (time from end of injection of local anesthetic or intravenous fentanyl till reaching VAS \leq 4) by 15 degrees leg raising test. The 15 degrees leg raising test will be used after 10 minutes in the groups received regional analgesia and 2 minutes in the fentanyl group. We will try to elevate the patient's leg for 15 degrees. If the patient complains of pain on moving his leg, the test will be aborted and we will wait for a minute before repeating the test.
- Patient's satisfaction score.
- Anesthesiologist satisfaction score for patient's positioning.
- Possible complications of spinal anesthesia, regional blocks and parenteral fentanyl.

- Time of first rescue analgesia (the time between complete injection of the local anesthetic in the regional groups or fentanyl injection and the first analgesia requested by the patient) and total postoperative rescue analgesic consumption in first 24 hours postoperative.
- Time of onset of postoperative ambulation (time from end of surgery till first ambulation by the patient).
- Duration of spinal anesthesia (time from end of injection of intrathecal hyperbaric bupivacaine till offset of spinal anesthesia effect detected by degree 0 on modified bromage score and return of fine touch detected by sensing pin bricks).

- **Statistical analysis:**

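### The pre-spinal leg-raise test has no maximum wait, and failure is recorded only during positioning, so a patient who never reaches VAS ≤ 4 has no failure record, onset time or stopping point

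*Protocol*

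**What the plan says.** The relevant rules are spread over four parts of the Protocol, section II (*Operational design*).

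- **Onset of analgesia (after the Group F description).** In all three groups a passive 15-degree leg raise is tried, first at 10 minutes after a block or 2 minutes after fentanyl. If the pain is intolerable, "the test will be aborted and we will wait for a minute before repeating the test". The repeat rule is "The test will be repeated every minute until we detect the onset of the analgesia", with onset defined as dynamic VAS ≤ 4. No maximum time or number of attempts is given.
- **Condition for positioning.** The same part says that once VAS ≤ 4, "patient will be positioned to receive spinal anesthesia". *Administration of spinal anesthesia* adds that the sitting position follows "After analgesia is established and fluid preload is given".
- **Failure and rescue (*Administration of spinal anesthesia*).** If VAS is ≥ 4 during positioning, "the procedure will be stopped, the patient will be recorded as a failure rate", and 1 mic/kg of intravenous fentanyl is given whatever the group. This is the only failure rule and the only rescue stated before the spinal.
- **Onset time (*Collecting data*).** The item is defined as "Onset time of the analgesic technique (time from end of injection of local anesthetic or intravenous fentanyl till reaching VAS" ≤ 4, judged by the leg raise.

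The only other stated way out is under *Withdrawal criteria*: "The patient has the right to withdraw from the study at any time". That is a patient's right, not a record of analgesic failure.

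**The concern.** The failure rule is placed after a step that the worst failures may never reach. A patient who gets to VAS ≤ 4 and then hurts on sitting up is counted as a failure and rescued. A patient whose analgesia never works at all is neither counted nor rescued under the written rules.

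Three things are at stake:

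- **Failure rate.** The recorded rate would be too low in any group that contains such a patient.
- **Onset time.** This is a listed data item, and it has no value for that patient.
- **Burden.** A patient over 65 with a hip fracture faces a series of painful tests. Each test can be stopped, but the series has no end.

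A statistical analysis plan could say how to handle a missing onset time. It cannot tell the bedside team when to stop testing, when to rescue, or whom to record as a failure. Those are procedures that the protocol fixes itself.

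**Working it through.** The protocol states no figure on this point, so the check is mainly a trace of the procedure, followed by some bounding arithmetic.

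**Trace for a patient who never reaches VAS ≤ 4.** The result depends on what VAS means in the condition for positioning. The protocol separates resting from leg-raise VAS at baseline and says dynamic VAS when it defines onset, but says only VAS when it gives the condition for positioning.

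1. *Dynamic VAS.* This is the natural reading, because onset is defined by dynamic VAS and positioning follows established analgesia. The patient fails the first leg raise and is retested each minute. The condition is never met, so positioning never starts, the failure rule cannot apply and rescue fentanyl is not triggered. Onset time has no end point.
2. *Resting VAS.* A patient with VAS ≤ 4 at rest but poor analgesia on movement is positioned. If VAS is ≥ 4 during positioning, the failure is recorded and rescue is given. The uncounted group shrinks to patients whose resting VAS stays above 4.

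Under both readings some patients fall outside the failure rule; the second makes the group smaller.

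**Effect on a group's recorded failure rate.** Inputs: 17 patients per group (*Sample size*); m never-responders; k failures recorded during positioning.

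- If all 17 stay in the denominator, the shortfall is (k + m)/17 − k/17 = m/17. For m = 1, 2, 3 this is 5.9, 11.8 and 17.6 percentage points.
- If one never-responder also drops out of the denominator, the shortfall is (k + 1)/17 − k/16 = (16 − k)/272. For k = 0, 3, 8 this is 5.9, 4.8 and 2.9 points.

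The figure of 5.9 points per patient therefore depends on keeping all 17 in the denominator.

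**Number of tests.** With one test per minute and no time allowed for the test itself (an upper bound), the count by minute t is t − 10 + 1 after a block and t − 2 + 1 after fentanyl.

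- t = 30: 21 after a block and 29 after fentanyl.
- t = 60: 51 and 59.

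**Could such a patient plausibly occur?** The documents give no non-response rate. Assume a common rate p across the 51 patients:

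- p = 2%: 17p = 0.34 expected per group; 1 − (1 − p)^51 = 64% chance of at least one in the trial.
- p = 5%: 0.85 per group; 93%.
- p = 10%: 1.7 per group; 99.5%.

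These figures follow from the assumed p and are not estimates. They show only that the case is worth a rule.

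**The case against.** The case for leaving the text alone has several parts.

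- **The undercount rests on one reading.** This stands in part. The condition for positioning does not say dynamic, so the full gap is conditional. The other text favours the dynamic reading, and the resting reading narrows the gap without closing it.
- **The consequence is modest.** This also stands. Failure rate is neither an objective nor an item under *Collecting data*; onset time is a data item but is not named in the objectives. The repeated scores would show that a patient did not respond, though no rule classes that patient as a failure.
- **Analysis rules may be elsewhere.** A reader might infer that the onset comparison will contain responders only. The protocol cannot establish that, because an analysis plan that is not shown could already censor these patients.
- **Waiting is deliberate.** On the ward a patient with VAS ≥ 4 "or complains of intolerable pain, a rescue analgesia will be given in the form of nalbuphine 0.1 mg/kg", while before the spinal the same complaint brings another wait. It is tempting to read this as inconsistent care. The settings differ: the leg raise provokes brief pain while analgesia is developing, and an early analgesic would spoil the onset measurement. Only the open end of the wait is a gap.
- **Clinicians would step in anyway.** Probably, and an hour of minute-by-minute testing is unlikely in practice. But the timing and labelling would then be ad hoc and could differ between patients or groups, which is a reason to state the rule.

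**Conclusion.** The point holds in conditional form. Read with dynamic VAS as the condition for positioning, the protocol leaves a never-responder with no failure record, no onset time, and no stopping point or rescue. Read with resting VAS, the same gap applies only to patients whose resting VAS stays above 4. The size is 5.9 percentage points of a group's recorded failure rate per such patient, provided that all 17 remain in the denominator.

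A reader might go further and infer that the comparison between groups is biased, perhaps in favour of one technique. The documents do not support that. They give no non-response rate for any group, so neither the frequency nor the direction of a difference can be derived, and the assumed 2%, 5% and 10% say nothing about either. This is a procedural gap worth closing; it does not show that the trial's comparisons are invalid.

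**What to change.** State in the onset-of-analgesia part a maximum wait, counted from the end of injection, which is already the starting point for onset time. The investigators choose its length. A common limit in the three groups keeps the failure rates comparable. Because fentanyl testing starts at 2 minutes, a limit long enough for the blocks could mean many leg raises in that group; fewer repeat tests there would limit the burden, at the price of a coarser onset time.

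At the limit:

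1. Stop testing and record the last leg-raise VAS before any added analgesic.
2. Give the fentanyl rescue already specified for positioning, or other care that the investigators choose.
3. Count the patient as an analgesic failure together with those who fail during positioning, with all randomised patients in the denominator.
4. Treat onset time as not reached, censored at the limit, and report the number of never-responders per group. This handling may sit in the analysis plan; steps 1 to 3 belong in the protocol.

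Say also whether the condition for positioning is dynamic or resting VAS.

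The change does not supply an unrescued positioning VAS for these patients, so the positioning VAS and operator-score comparisons remain conditional on reaching VAS ≤ 4. The cost is a few lines of text, one extra field on the record form and a slightly higher stated failure rate.
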